### Sample size and statistical considerations:

We will recruit 10 subjects, and each subject will undergo PET evaluations at day 0 (baseline), day 5, day 28, day 90 and day 273. The change with time in PET uptake in the lesional and normal appearing white matter, cortical and subcortical grey matter, and peri-plaque area of chronic lesions will be estimated using an analysis of response profiles model including a categorical effect of time and an unstructured covariance matrix for the residuals. This approach allows any change with time and places no structure on the covariance matrix. The primary analysis will be the global comparison across the five time points. If a significant difference among the five time points is observed, we will estimate the

change between day 0 and each of the other measurements, and we will correct for four multiple comparisons using a Bonferroni correction. Since the analysis of response profiles model estimates the parameters using maximum likelihood with the *mixed* command in Stata, this approach will handle missing data that is missing at random. Therefore, subjects who are missing one or more measurement will be included in our analysis. A p-value  $<0.05$  will be considered statistically significant.

In addition to the primary analysis of the change with time, we will also compare the change in PET uptake with the change in other measured variables (MRI, clinical, and immunologic measures). All of the remaining variables will be measured at the same time points as PET uptake (days 0, 5, 28, 90 and 273). First, we will calculate the change from day 0 to each of the other time points for each of the measures, and we will estimate the correlation between the changes using Pearson's correlation coefficient. This analysis will fit several models, but the interpretation of these correlations will be easy to interpret. Second, we will fit a linear mixed model with PET uptake as the outcome and two predictors for each of the other measured variables. In particular, we will include (1) the day 0 measure and (2) the change from day 0 so that we can estimate both the cross-sectional and longitudinal association between the other measured variables and PET. Our focus will be the longitudinal association estimated using the second term. If a subject receives corticosteroids during the study period, we'll account for that in a multivariate analysis by adding it as a covariate.

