#### Sample size calculation:

No prior data regarding effect of Ofatumumab on microglial changes is available at this time. The sample size of 10 is based on the typical number of patients in published PET-MRI studies with the same tracer. With a sample size of 10 subjects, we will be able to estimate the mean change between any pair of time points with a standard error of 0.32 times the standard deviation of the change. Assuming a PET effect size of 1.1 noticeable in intracortical and leukocortical lesions, identified on combination of PET and 3T MRI, a sample size of 10 provides 85% power and alpha-error of less than 5% to detect a treatment response. This means that we will have a reasonable precision for the design of future studies.

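### Holm's step-down would be a cheap improvement on plain Bonferroni for the four day-0 contrasts, although the planned correction is valid

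*Combined protocol and SAP*

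**What the plan says.** The section Sample size and statistical considerations sets the design: "We will recruit 10 subjects, and each subject will undergo PET evaluations at day 0 (baseline), day 5, day 28, day 90 and day 273". PET uptake is modelled with time as a categorical effect and an unstructured covariance. "The primary analysis will be the global comparison across the five time points". The visit contrasts are conditional on that test: only when it is significant is the "change between day 0 and each of the other measurements" to be estimated. On multiplicity among these contrasts the plan says: "we will correct for four multiple comparisons using a Bonferroni correction". A p-value below 0.05 "will be considered statistically significant"; sidedness is not stated. The model "estimates the parameters using maximum likelihood with the" Stata mixed command, and no small-sample degrees of freedom are given.

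The biostatistical section mentions no step-down method, gives no reason for choosing Bonferroni and does not mention confidence intervals. The Sample size calculation section takes its effect size from another setting ("Assuming a PET effect size of 1.1 noticeable in intracortical and leukocortical lesions"), states 85% power, and presents n = 10 as giving useful precision for planning later studies.

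**The concern.** Specific Aim 2 is the time course of the effect, and the primary endpoint names both early and late time points. Which visits differ from baseline is therefore a question that the study sets out to answer. Plain Bonferroni holds every contrast to 0.0125, however clearly the other visits have changed. Holm relaxes the threshold after each rejection and keeps the same error ceiling. With 10 subjects, a visit that has truly changed may be declared unchanged under Bonferroni when Holm would have detected it. At stake is some sensitivity in describing the time course, not the validity of the analysis.

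**Working it through.** **Inputs from the plan.** n = 10; four contrasts with day 0; alpha 0.05; effect size 1.1, read as mean change divided by SD of change.

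**Assumptions, not in the plan.** Two-sided tests; equal correlation between the four changes of 0.3, 0.5 or 0.8; complete data; paired t contrasts; an exact Hotelling test at 0.05 as the global gate.

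**1. The plan's own figures.** The standard error is 1/√10 = 0.316 SD, matching the stated 0.32. For power with n = 10, d = 1.1 and alpha 0.05, a two-sided paired t-test gives 87.1% and a two-sided Wilcoxon signed-rank test gives 85.3% by simulation. The stated 85% is thus reproduced by the signed-rank test; the plan does not name the test. It is a single-comparison figure at 5%, not a claim about corrected contrasts.

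**2. The thresholds.** Bonferroni uses 0.05/4 = 0.0125 for each contrast. Holm orders the p-values and compares them in turn with 0.05/4 = 0.0125, 0.05/3 = 0.0167, 0.05/2 = 0.025 and 0.05, stopping at the first failure. Paired t power at d = 1.1 for a single contrast at these thresholds is 64.6%, 69.9%, 77.0% and 87.1%.

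**3. Why the ceiling is the same.** If m of the nulls are true, the first true null that Holm can reject is tested at no more than 0.05/m. By the union bound the chance of any false rejection is at most m × 0.05/m = 0.05, whatever the dependence. Every Holm threshold is at least 0.0125, so Holm rejects everything that Bonferroni rejects. The first step is identical, so the chance of at least one rejection is identical.

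**4. Unused error under the plan.** If any visit has truly changed, at most three nulls are true, so Bonferroni spends at most 3 × 0.0125 = 3.75%.

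**5. Size of the gain.** Simulated trials with the gate applied, power per truly changed visit:

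| Visits changed | Change | Correlation | Bonferroni | Holm |
|---|---|---|---|---|
| Four | 1.1 SD | 0.3 | 57% | 68% |
| Four | 1.1 SD | 0.5 | 52% | 60% |
| Four | 1.1 SD | 0.8 | 45% | 50% |
| Three | 1.1 SD | 0.5 | 59% | 66% |
| Two | 1.1 SD | 0.5 | 59% | 62% |
| One | 1.1 SD | 0.5 | 52% | 52% |
| Four | 0.5 SD | 0.5 | 6.5% | 7.9% |

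If all four visits change by 1.1 SD, the chance of detecting all four rises from 29% to 51% at correlation 0.5, and from 35% to 47% at 0.8. In no simulated trial did Bonferroni reject where Holm did not.

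**6. Realised error.** With some visits changed and others not, gated family-wise error was about 1 to 3% for Bonferroni and about 3 to 4% for Holm. Both are below 5%.

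**7. Dependence on valid p-values.** Suppose maximum-likelihood variances (divisor n, not n − 1) were used with normal reference values; this is an assumption, because the plan is silent. The true size of a nominal 0.0125 contrast is then 2 × P(t with 9 df > 2.498 × √(9/10)) = 4.2%. Ungated family-wise error with two true nulls becomes 7 to 8% for Bonferroni and 9 to 11% for Holm.

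**The case against.** The case for leaving the text alone is respectable, and much of it stands.

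- Bonferroni is valid and pre-specified, and nothing in the documents contradicts it. A reader might infer that it is an error, or that it breaks the 85% power statement. Neither follows, because that statement concerns one treatment response at 5%.
- A reader might infer that power is given away for nothing. That is too strong. Bonferroni yields simple simultaneous intervals that match its tests (half-width 0.98 SD, against 0.72 SD unadjusted), which suits a pilot that stresses estimation and precision. Against this, the plan never says that it will report such intervals, and intervals computed only after a significant gate carry no simple simultaneous guarantee.
- The contrasts are a conditional follow-up. The primary test does not move.
- The gain depends on several visits changing by a large amount. The effect of 1.1 comes from cortical lesion findings, and the plan says that no prior data exist for ofatumumab on microglia. A full change already at day 5 is the most favourable case; the Background reports peripheral B-cell depletion of only 50% by week 2.
- Larger gains can be computed without the gate (65% to 77% with four changed visits at correlation 0.5), but the plan gates, so those figures do not describe it.
- If p-values are not corrected for the small sample, Holm adds false rejections. That weakness affects both methods and matters more than the choice between them.

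**Conclusion.** This is an optional, low-cost improvement. With valid p-values, Holm dominates Bonferroni for testing the four contrasts. The gain per changed visit at 1.1 SD is about 4 to 11 points if all four visits change, 6 to 7 if three, 3 if two and 0 if one; it is about 1 point at 0.5 SD in all four. These sizes rest on the assumed effect, correlations, paired t contrasts and Hotelling gate, and would differ under the fitted mixed model or with missing scans. The dominance itself needs only valid p-values, which the maximum-likelihood wording does not yet secure. It would go too far to say that the plan will miss changed visits: that happens only if more than one visit has truly changed, apart from a negligible effect with a single one. The error rates are also not the same. The two methods share the 5% ceiling, and Holm's realised rate lies closer to it.

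**What to change.** In Sample size and statistical considerations, replace the Bonferroni correction with a Holm step-down correction for the four day-0 contrasts, and state that it is applied to p-values computed with small-sample degrees of freedom. If intervals are to be reported, add that they are unadjusted 95% confidence intervals for estimation only. Make the change before the data are analysed.

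The cost is a short edit and the ordering of four p-values, with no extra subjects or scans. There are two downsides to accept. Holm has no equally simple matching simultaneous intervals, so an unadjusted interval may exclude zero when the Holm test is not significant. Realised family-wise error also moves nearer to 5%, while staying at or below it.

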Paired t-test and repeated measures ANOVA analyses will be performed to assess differences in PET measures over time. Correlation analyses will be performed between PET and MRI measures and clinical variables. We will also look for correlations between changes in PET uptake and peripheral CD19 counts at various time points of the study.

Statistical analyses will be performed using Stata version 16 (StataCorp, College Station, Texas, USA).

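### The primary global test uses maximum likelihood with an unstructured 5x5 covariance in 10 subjects and names no small-sample reference; against the usual chi-square its type I error per region is 16.5% (likelihood ratio) or 33.2% (Wald), not 5%

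*Combined protocol and SAP*

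**What the plan says.** In the Combined protocol and SAP, under 'Sample size and statistical considerations', the design is fixed: "We will recruit 10 subjects, and each subject will undergo PET evaluations at day 0 (baseline), day 5, day 28, day 90 and day 273". Uptake in each brain region is modelled with "a categorical effect of time and an unstructured covariance matrix for the residuals". On inference the section says "The primary analysis will be the global comparison across the five time points". If that test is significant, day 0 is compared with each later visit, and "we will correct for four multiple comparisons using a Bonferroni correction". The stated level is p<0.05.

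The fitting method is given as one that "estimates the parameters using maximum likelihood", through Stata's mixed command. It is offered as the reason that incomplete data can be handled: "subjects who are missing one or more measurement will be included in our analysis".

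The same section later adds: "Paired t-test and repeated measures ANOVA analyses will be performed to assess differences in PET measures over time". These analyses are not called primary and are not linked to the two-step rule. 'Sample size calculation' claims an alpha error below 5%.

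Nothing in these sections says whether the global test is Wald or likelihood ratio, or which distribution its p-value comes from. No REML fit, Kenward-Roger or Satterthwaite adjustment, or Hotelling F is mentioned.

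**The concern.** The model estimates 5 means and 15 covariance parameters from 10 subjects. The large-sample reference for a likelihood-based test treats the covariance as if it were known. Here it is estimated very imprecisely, and maximum likelihood also biases it downwards, so the test statistic is too large too often.

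The study has no control arm, so this within-subject test carries the whole primary inference. If its p-value is wrong, a finding that ofatumumab changes microglial activation could be declared far more often than the stated level allows. The intervals meant to inform future studies would also be too narrow.

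**Working it through.** **Inputs.** From 'Sample size and statistical considerations': n = 10 subjects, 5 visits (so p = 4 changes from day 0), unstructured covariance, maximum likelihood (ML), nominal level 0.05, and four contrasts at 0.05/4 = 0.0125. From 'Sample size calculation': effect size 1.1, standard error 0.32 SD, power 85%. Assumed, because the plan is silent: chi-square and z references, normal data and, except in step 6, no missing scans.

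**1. The plan's own figures.** The standard error is 1/√10 = 0.316 SD, which matches 0.32. Power for one mean change with d = 1.1 and n = 10 is 87.1% by a two-sided 5% paired t-test. It is 85.1% with the sample size deflated to 10 × 3/π for a signed-rank test. The stated 85% is therefore about right for one change tested at 5%. It says nothing about the global test.

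**2. Exact null distribution of the global test.** For complete normal data, Hotelling's statistic on the four changes is

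- T² = [4 × 9/6] × F(4,6) = 6 F(4,6)
- ML Wald = T² × 10/9 = 6.667 F(4,6)
- ML likelihood ratio (LR) = 10 ln(1 + T²/9)

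The chi-square(4) 95% point is 9.488.

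- Wald: reject if F > 9.488/6.667 = 1.423; P = **0.332**.
- LR: reject if T² > 9(e^0.9488 − 1) = 14.24, so F > 2.374; P = **0.165**.
- The F(4,6) 95% point is 4.534, so the cut-offs that would give 5% are 6.667 × 4.534 = 30.2 (Wald) and 10 ln(1 + 6 × 4.534/9) = 13.9 (LR).

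These results do not depend on the true covariance. Simulation with 200,000 trials under each of three covariance structures gave 33.1-33.2% and 16.4-16.5%.

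**3. Partial repairs do not work.**

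| Fit and reference | Type I error |
|---|---|
| ML LR, chi-square(4) | 16.5% |
| ML Wald, chi-square(4) | 33.2% |
| REML Wald, chi-square(4) | 29.3% |
| ML Wald/4 on F(4,9) | 18.8% |
| REML Wald/4 on F(4,9) | 16.0% |
| T²/6 on F(4,6) | 5.0% |

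**4. Follow-up contrasts with a z reference.** The ML standard error is √(9/10) of the usual one. Each contrast therefore has true error P(|t₉| > 2.498 × 0.949 = 2.370) = 0.042, against the intended 0.0125. A z-based 95% interval covers P(|t₉| < 1.960 × 0.949 = 1.859) = 90.4%.

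**5. Global test significant and at least one visit named, no true change.** There were 100,000 simulated trials for each of eight assumed covariances: exchangeable 0.3, 0.7, 0.9; AR(1) by visit 0.5, 0.7, 0.9; exponential decay in days (tau 100) with a 0.05 nugget; and exchangeable 0.7 with SDs 1, 1, 1.2, 1.5, 2.

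| Rule | Chance of naming a visit |
|---|---|
| LR, then z | 6.8-8.8% |
| Wald, then z | 10.6-13.5% |
| LR, then paired t | 3.5-4.3% |
| Wald, then paired t | 4.0-4.9% |
| Exact F, then t | 1.5-2.0% |

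**6. Missing scans.** The plan gives no dropout rate. As an illustration, 2 of 10 subjects miss day 273 at random and stay in the fit (exchangeable 0.7, 4,000 trials). Error is then 20% (LR) and 41% (Wald).

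**The case against.** The strongest reply is that the plan never commits to chi-square. The maximum likelihood sentence is there to justify the handling of missing data, and an analyst could still apply a sound reference. That is true, and the 16.5% and 33.2% are conditional on the large-sample reference. But that is the usual reference for an ML fit, and nothing in the text points elsewhere. Leaving the choice open until the data are seen is itself a defect, and two plausible small-sample substitutes in the working still give 16.0% and 18.8%.

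Second, the SAP also lists repeated measures ANOVA, which is a global test with a finite-sample F. With complete null data its error was about 5-8% without a sphericity correction across the assumed covariances. The chance that it and the primary test both reject was about 4-5% (LR) or 5-7% (Wald). So a false primary result would often be contradicted by another planned analysis. The paired t-test is exact for complete normal data and helps in the same way. But neither is primary or required by the two-step rule, no sphericity correction is stated, and ANOVA would drop incomplete subjects. They limit the harm without repairing the primary test.

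Third, this is a 10-subject pilot, its complete-data point estimates are unaffected, and the risk of wrongly naming a visit is well below the headline rates. All of that is fair. The plan nevertheless makes the global p-value its primary result and claims an alpha below 5%.

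Two limits on the remedy also stand. The exact benchmark covers complete data only, and REML with Kenward-Roger was not simulated here with missing scans. Keeping the unstructured covariance is a choice: a structured covariance fixed in advance, with a degrees-of-freedom correction, is a reasonable alternative.

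**Conclusion.** The concern holds and should be fixed before analysis. As written, the primary test has no defined reference distribution. Under the usual one, its error per region is about three times (16.5%) to more than six times (33.2%) the nominal 5%. These two figures are exact for complete normal data. The rates for naming a visit rest on the assumed covariances, and the missing-data figures illustrate one pattern only. Confidence is high.

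**What to change.** Replace the maximum likelihood sentence with wording such as:

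> *The model will be fitted by restricted maximum likelihood with an unstructured covariance. The 4-df global test and the four changes from day 0 (each at 0.0125) will use Kenward-Roger F and t reference distributions.*

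Both parts are needed, because REML with chi-square still gives 29.3%. For complete data the results should match Hotelling's T² on F(4,6) and t on 9 df for each change, which gives a ready check of the code. Name one simpler covariance in advance, with the same correction, in case the unstructured fit does not converge. State whether the paired t-tests and ANOVA are supportive only. REML keeps the missing-at-random handling and the subjects with missing scans.

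The cost is a few sentences and a model option, with no new data. The real price is power. Take 1.1 as mean change over SD of change and assume exchangeable correlation. The noncentrality is then 10 × 2 × [Σδ² − (Σδ)²/5], with δ the four standardised changes:

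| Pattern of change | Noncentrality | Power, exact F(4,6) |
|---|---|---|
| 1.1 at all four visits, or at day 273 only | 19.36 | 67% |
| Equal steps by visit up to 1.1 | 15.13 | 56% |
| 1.1 at the last two visits only | 29.04 | 85% |

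The corrected two-step rule is also conservative, naming a visit in only 1.5-2.0% of null trials. If that loss is unwelcome, the remedy is a simpler covariance or a single primary contrast, chosen now and not after the data are seen.

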#### Rationale and potential benefits

There has been an increasing recognition of the role of B-cells in the pathogenesis of MS since the initial description of intrathecal immunoglobulin synthesis in 1950. In MS, B-cells are present in parenchymal

lesions, tertiary follicle like structures in the meninges and cerebrospinal fluid where they are known to undergo clonal expansion. B-cell directed therapies using anti-CD20 antibodies have been shown to be highly efficacious in preventing relapses in RRMS and slowing progression in primary progressive MS although their mechanisms of action are not clear. In animal models, targeting B-cells using antiCD20 antibodies led to reduction in microglial activation and lesion formation. In fact, there was greater effect of anti-CD20 antibodies on microglial activation and lesion formation in the antibody independent model implying that the mechanism of action of these therapies extends beyond antibody production and may involve their actions on microglia. However, there is no human data to date exploring this hypothesis. Ofatumumab is a fully human anti-CD20 antibody that has recently been studied for treatment of relapsing MS in multiple phase II and phase III randomized controlled trials (ASCLEPIOS I and II).

Prior studies using Ofatumumab have demonstrated the time course of B-cell depletion in the periphery. There was 50% reduction by week 2, and >80% reduction by week 4 after administration of Ofatumumab at various doses. Ofatumumab demonstrated high efficacy for relapse rate reduction, new lesion formation and serum neurofilament light chain level reduction in multiple sclerosis patients as compared to an active comparator arm of teriflunomide (Aubagio). Additional secondary endpoints were also met, where ofatumumab showed a relative risk reduction in both 3-month confirmed disability (CDP) and in 6-month CDP versus teriflunomide in a pre-specified pooled analysis. Ofatumumab was found to be safe in MS patients.

However, the effects of Ofatumumab on microglia in the brain in MS patients are not known at this time. It is important to study the effect of anti-CD20 therapies on the innate immune system to understand their role in limiting disease progression in MS. We aim to assess the relationship between peripheral B-cell depletion and changes in microglial activation, after administration of Ofatumumab.

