### **Specific Aims:**

Specific Aim 1: To determine the effect of Ofatumumab on microglial activation in MS over 9 months.

Specific Aim 2: To determine the time course of effect of Ofatumumab on microglial activation and its relationship with peripheral B-cell depletion, serum neurofilament light (sNFL) chain and glial-fibrillary acid protein (GFAP) levels and other serum biomarkers

Specific Aim 3: To determine the relationship of PET changes following Ofatumumab initiation with 3T MRI changes and clinical parameters.

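### The PET-marker mixed model lists no visit term, so its CD19 change coefficient cannot separate parallel time trends from an individual-level link

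*Combined protocol and SAP*

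**What the plan says.** Three analyses appear under 'Sample size and statistical considerations'.

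- **Primary PET model:** an "analysis of response profiles model including a categorical effect of time", with unstructured residual covariance.
- **PET against other markers, step 1:** "First, we will calculate the change from day 0 to each of the other time points for each of the measures", followed by Pearson correlations between the changes.
- **PET against other markers, step 2:** "we will fit a linear mixed model with PET uptake as the outcome and two predictors for each of the other measured variables". For each marker, "we will include (1) the day 0 measure and (2) the change from day 0". The plan adds: "Our focus will be the longitudinal association estimated using the second term". The only further covariate named is corticosteroid use.

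On timing, "All of the remaining variables will be measured at the same time points as PET uptake". Aim 2 concerns the "time course of effect of Ofatumumab on microglial activation and its relationship with peripheral B-cell depletion", and the first secondary endpoint names CD19 count, GFAP and neurofilament light. The study has one arm of 10 subjects, all treated. For the expected B-cell course, the section 'Rationale and potential benefits' says: "There was 50% reduction by week 2, and >80% reduction by week 4".

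**The concern.** The text names time for one model and not for the other, so an analyst who follows it would fit the marker model without visit. The model is only sketched and a visit term may be intended, but nothing says so.

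The change coefficient is the one the plan will interpret. Without visit it pools two different statements: (a) PET and CD19 both moved after treatment began, and (b) subjects whose CD19 fell further had a larger PET change. With no untreated group and a steep B-cell fall common to everyone, (a) alone can make the coefficient significant.

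The risk is that a result supporting only (a) is reported as (b). The study is presented as a basis for designing later ones, so that reading could carry forward. The problem needs a trend in both mean PET and the marker. It is severe for CD19 and smaller for markers that barely move.

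**Working it through.** **The plan's own figures.** None concerns the marker model. The stated standard error of 0.32 SD is 1/√10 = 0.316. The stated 85% power at effect size 1.1 compares with 87.1% for a two-sided paired t-test and 85.1% for a Wilcoxon approximation. Nothing below depends on these.

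**Why the coefficient picks up the shared trend.** Let D_ij be subject i's marker change at visit j, with visit means d_j, and let m_j be the common PET shift. With no individual link, the within-subject slope has expectation close to

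Σ_j (d_j − d̄)(m_j − m̄) / Σ_j (d_j − d̄)²

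This is non-zero whenever the two average curves move together. A categorical visit term removes d_j and m_j, leaving only differences between subjects at the same visit.

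**Inputs.** From the documents: n = 10, five visits, CD19 entry floor of 110 cells/µL, B-cell fall above 80% by week 4. Assumed:
- PET: subject intercept SD 1; noise such that the SD of change is 1 (variance 0.5 per visit).
- Baseline CD19: lognormal, median 220, log-SD 0.35.
- CD19 fraction remaining: U(0.4, 0.9) at day 5, U(0, 0.2) at day 28, U(0, 0.05) later.
- Random intercept (the plan states no random-effects structure).

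The sample size section does not define its 1.1 as SD of change; it is used here only as an illustration.

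**Hand check, percentage CD19 change.**
- Mean remaining fractions are 0.65, 0.10 and 0.025, so d = −(0, 0.35, 0.90, 0.975, 0.975). Deviations from the mean: 0.64, 0.29, −0.26, −0.335, −0.335. Their sum of squares is 0.786.
- PET step of −0.5 from day 28: deviations 0.3, 0.3, −0.2, −0.2, −0.2. Sum of products: 0.192 + 0.087 + 0.052 + 0.067 + 0.067 = 0.465.
- Slope = 0.465/0.786 = 0.59 PET units per 100% depletion, with no individual link present.
- SE = √(0.5/(10 × 0.786)) = 0.252, so z = 2.35. Rejection probability ≈ Φ(2.35 − 1.96) = 65%. Simulation gives 63.7%.
- PET fall linear in days, −0.5 by day 273: sum of products 0.233, slope 0.297, z = 1.18, rejection about 22%. Simulation gives 22.2%.

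**Simulation, no individual link** (4,000 trials per row, maximum likelihood, Wald z): share of trials with a significant CD19 change term.

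| Common PET shift (SD of change) | Absolute, no visit | Absolute, visit | Percentage, no visit | Percentage, visit |
|---|---|---|---|---|
| None | 6.4% | 7.5% | 6.4% | 6.6% |
| Step −0.25 | 21.4% | 8.0% | 22.5% | 7.9% |
| Linear in days −0.5 | 20.3% | 7.3% | 22.2% | 7.8% |
| Ramp by visit −0.5 | 33.4% | 7.0% | 36.1% | 7.9% |
| Gradual −0.5 | 43.4% | 6.9% | 46.4% | 7.8% |
| Step −0.5 | 59.6% | 7.6% | 63.7% | 7.4% |
| Linear in days −1.1 | 60.9% | 7.6% | 65.9% | 7.7% |
| Ramp by visit −1.1 | 89.8% | 8.5% | 92.8% | 7.2% |
| Step −1.1 | 99.6% | 8.1% | 99.9% | 8.2% |

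The small excess over 5% in the visit columns is present with no PET shift too. The shared visit mean is 89% of within-subject variance in absolute CD19 change and 98% in percentage change.

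**Sensitivity.**
- Five other CD19 assumption sets, −0.5 step or linear, absolute change: 13–62% without visit, 7–9% with it.
- A separate simulation (baseline mean 250, SD 80; mean depletion 30/85/95/97%; REML): 5%, 24%, 49%, 83% and 99% for shared falls of 0, 0.3, 0.5, 0.8 and 1.1. With visit: 4–6%.
- Other markers without visit: 9–17% for a 10% marker fall and 19–62% for a 30% fall. With visit, across markers: 7–9%.
- By-visit Pearson tests at step −1.1: 4.5–5.4%.

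**What adjustment costs and does not cure.**
- The SE of the CD19 slope rises about 3-fold for absolute change (2.3–4.0 across sets) and about 6-fold for percentage change (5–12).
- Power for a true link of 1.1 PET units per 220-cell fall goes from 99.6% to 42%. For 1.1 per 100% depletion it goes from 99.2% to 15%, because about 84% of the visit-centred variation in percentage change sits at day 5.
- After subject and visit means are removed, about 81% of the variation in absolute CD19 change reflects baseline CD19 (64–93% across sets). If PET change depends on baseline CD19 only (0.3, 0.5 or 0.8 PET units per SD of baseline), the adjusted absolute term rejects in 24%, 45% and 72% of trials. The adjusted percentage term stays at 7–8%.

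**The case against.** The strongest reply is that co-movement is what Aim 2 asks for. It speaks of a time course and its relationship with depletion, and in a single-arm study that is a legitimate target. On that reading a significant unadjusted term is no error, and visit adjustment removes most of the signal. This stands as far as it goes: the rejection rates above are errors only for a claim about individual depth of depletion. The plan does not say which reading it will report, so the point is about labelling as much as modelling.

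Second, the by-visit Pearson correlations already address the individual-level question and match the wording of the secondary endpoint. That is correct, and they should stay. They do not change what the mixed-model coefficient means, and the plan makes that coefficient the focus of the model.

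Third, the size rests on assumptions from outside the documents, and with no PET trend there is no problem. Also true. The exact rates depend on the assumptions. The direction does not, given the expected CD19 fall, and a PET trend is what the primary analysis looks for.

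Fourth, the adjusted model is imprecise and adds fits across several brain regions in a 10-subject pilot. This stands as a limit on what the adjusted result can show. It does not support reading the unadjusted term as individual-level evidence, since much of its precision comes from the shared trend.

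**Conclusion.** The concern holds. As written, the CD19 change coefficient mixes a time course common to all subjects with any individual link. Under the assumed CD19 and PET distributions and no individual link, it is significant in 20–60% of trials for a 0.5 SD mean PET fall and in 61% to over 99% for 1.1 SD, against 7–9% with categorical visit. Expressing CD19 as percentage change without visit does not help (22–64% at 0.5 SD). The confounding follows from the listed terms, the single-arm design and the expected B-cell fall. Its size depends on the assumed distributions, a random intercept and the presence of a PET trend. It is a gap in a sketched secondary analysis; the primary PET analysis is untouched. It should be corrected before analysis.

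**What to change.** In the SAP text for the marker model:

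1. Keep the planned model, and state that its change coefficient describes co-movement over time.
2. Report beside it the same model with visit as a categorical fixed effect, with confidence intervals and labelled exploratory.
3. State that no claim that subjects with more depletion had more PET change will rest on the unadjusted term alone.
4. For CD19, also fit the visit-adjusted model with change as a percentage of baseline, and do not read the visit-adjusted absolute term alone as an effect of depletion depth. The percentage model is the least essential part of this list; the caution is needed either way.
5. State that a null visit-adjusted result with 10 subjects is weakly informative, and that neither version can establish mechanism.
6. Keep the by-visit Pearson correlations as planned.

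The cost is a few sentences and extra fits on data already to be collected, with the wide intervals shown above.
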